The broad objective of the studies proposed under this protocol is to use transcranial brain stimulation, methods of non-invasive brain stimulation, to address questions about the functional anatomy of the human brain. Under this protocol These stimulation techniques offer advantages over measurement techniques, such as electroencephalography (EEG) and functional magnetic resonance imaging (fMRI), in that they support inferences about causation, as opposed to correlation. The stimulation techniques covered by this protocol include transcranial magnetic stimulation (TMS) and transcranial current stimulation (tCS). Previous work carried out by the PI's group under protocol 2011-0608 (which the present protocol is intended to replace) indicates that TMS interacts in interesting ways with cortical oscillations, and therefore offers a unique way to study the function of these physiological phenomena. The experiments described in this protocol fall into several methodological categories: simultaneous TMS and fMRI; repetitive or single-pulse TMS, which is administered alone, simultaneously with EEG, or before fMRI scanning; and tCS, which is administered via a cap that also affords simultaneous EEG recording. In all cases, these studies follow from work that has been carried out by the PI's group under protocol 2011-0608. In all cases, the experiments carried out under this protocol will test hypotheses about the neural bases of human perception, attention, and memory. Specific experiments differ from one another in terms of the details of the cognitive task(s) that subjects perform, but not in terms of the general TMS and/or physiological measurement (i.e., fMRI or EEG) procedures that are used. For this reason, this protocol will follow the

convention used in 2011-0608, in which each experiment is described as a “sub-study” of the protocol.

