- B. Sub-study M.1 (TMS/EEG_motion): One 1 hr MRI visit for localization. Two 4 hr TMS/EEG sessions.
- C. Sub-study M.2 (TMS/EEG_motion_color): 1 hr MRI visit for localization. Two 4 hr TMS/EEG sessions.
- D. Sub-study T.1 (UMI1): three sessions (a training session in fMRI scanner, TMS/fMRI session targeting IPS, TMS/fMRI session targeting LASSO-identified cortex, each up to 2 hr in length.
- E. Sub-study T.2 (UMI2): three sessions (a training session in fMRI scanner, TMS/fMRI session targeting IPS, TMS/fMRI session targeting LASSO-identified cortex, each up to 2 hr in length.
- F. Sub-study U (EEG Training): One visit 3.75 hr for EEG session, 5 hours per week for 2 weeks of training on the material, and a subsequent 3.75 hr visit for a final EEG session.
- G. Sub-study O (Biacom EEG): One 2 hr visit for EEG session.
- H. Sub-study V (FREQMOD): One 1.5-hr visit for EEG session
- I. Sub-study W: One 1.5-hr visit for tCS session
- J. Sub-study X: One 2.5-hr visit for tACS session
- K. Sub-study Y (2Back EEG): One 2-hr visit for EEG session
- L. Sub-study Z: (SPACEORDEREEREG): One 3-4-hr visit for EEG session
- M. Sub-study AA: (SPACETIME EEG): One 3-4-hr visit for EEG session
- N. Sub-study AB: (LTM EEG): One 1-hr for behavioral session; Two 3-4 hr visits for EEG sessions
- O. Sub-study AC: (DACOM): One 3-4-hr visit for EEG session
- P. Sub-study AD: (MFE): One 3-4 hr visit for EEG session
- Q. Sub-study AE: (HAMS): One 4 hour visit for EEG session
- R. Sub-study AF: (PIII): One 4-hour visit for EEG session

7. **Subject Population:**

Below, the subject population is denoted for each sub-study:

- A. Sub-study L.3 (TMS/EEG_1D): 24 subjects
- B. Sub-study M.1 (TMS/EEG_motion): 24 subjects
- C. Sub-study M.2 (TMS/EEG_motion_color): 24 subjects
- D. Sub-study T.1 (UMI1): 24 subjects
- E. Sub-study T.2 (UMI2): 24 subjects
- F. Sub-study U (EEG Training): 24 subjects
- G. Sub-study O (Biacom EEG): 24 subjects
- H. Sub-study V (FREQMOD): 24 subjects
- I. Sub-study W: 24 subjects
- J. Sub-study X: 24 subjects
- K. Sub-study Y: 42 subjects
- L. Sub-study Z: 24 subjects
- M. Sub-study AA: 30 subjects
- N. Sub-study AB: 24 subjects
- O. Sub-study AC: 24 subjects
- P. Sub-study AD: 30 subjects
- Q. Sub-study AE: 25 subjects
- R. Sub-study AF: 20 subjects

*Note: 17 subjects from M.1 and 2 subjects from M.2 had been completed under 2011-0608. Therefore, total subject population for this protocol, 2016-0500, is 479.

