The aim of the study is to investigate the oscillatory and representational dynamics of contextual information in visual working memory. EEG data is recorded from a 60-channel cap connected to an Eximia 60-channel amplifier (Nextim, Helsinki, Finland) while subjects complete a working memory orientation recognition task. Each block consists of serial presentation of orientation grating stimuli with subjects indicating their memory for those stimuli. The experiment will take 3-4 hours in total.

6. Sub-study AA: (SPACETIME EEG)

The aim of the study is to investigate how spatial and temporal expectation of forthcoming visual stimuli modulate both behaviour and brain oscillations. EEG data is recorded from a 60-channel cap connected to an Eximia 60-channel amplifier (Nextim, Helsinki, Finland) while subjects complete a working memory orientation recognition task. Each block consists of serial presentation of orientation grating stimuli with subjects indicating their memory for those stimuli. The experiment will take 3-4 hours in total.

7. Sub-study AB: (LTM EEG)

The aim of the study is to shed light on the working memory-long term memory transfer mechanisms. EEG data is recorded from a 60-channel cap connected to an Eximia 60-channel amplifier (Nextim, Helsinki, Finland) while subjects complete a working memory orientation recognition task. Each block consists of presentation of dot-motion stimuli with subjects indicating their memory for those stimuli. The EEG portion of the experiment will take 6-8 hours in total, split over two sessions, with an additional 1-hour behavioral session.

8. Sub-study AC: (DACOM)

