The purpose of the study is to 1) investigate the trial-to-trial adaptive control of working memory in handling distraction from the discrimination stimuli, and 2) examine the neural correlates of the control processes in working memory, specifically testing the temporal and spatial characteristics of the control signal. EEG data are recorded from a Brain Products (brainproducts.com) actiCHamp Plus 64-channel high density EEG System while subjects complete a working memory dual-task paradigm. Each block consists of presentation of oriented Gabor patches, with an endogenous spatial cue indicating which of the two to memorize, and then they remember that orientation throughout the task, and recall the remembered orientation at the end of the trial. During the delay of the working memory task, another Gabor patch with varying levels of contrast will appear and participants will perform a psychophysical discrimination task on its orientation and report whether it is clockwise or counterclockwise compared to a vertical orientation. The experiment will take 3-4 hours in total.

9. Sub-study AD: (MFE)

The purpose of the study is to 1) find a neural marker of binding multiple features into VWM, and 2) investigate whether position information is an especially important feature for VWM binding. EEG data are recorded from a Brain Products (brainproducts.com) actiCHamp Plus 64-channel high density EEG System while subjects complete a typical visual working memory (VWM) task. Before memory array display, at the beginning of each trial, an arrow will be presented for 200 msec as a cue to notice either the left or right side of the memory array to be memorized. Four colored bars will be presented as the memory array then. The session will be separated into three block conditions to require participants to remember either Color and Orientation, Color and Position, or only Color in each block, respectively. At the end of each trial, one of the required features will be tested. All three blocks will be conducted with a counterbalanced order across participants. The experiment will take 3-4 hours in total.

10. Sub-study AE: (HAMS)

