This sub-study will build on the findings of sub-study K. Behavioral task will be completed while EEG is recorded from an EGI system 256 electrode cap. The task was about 1 hour, plus 1 hour of EEG setup. Subjects have to decide whether a briefly presented oriented grating is tilted to the left or the right and then rate their subjective visibility of that grating. On each trial, a color cue appears before the grating that indicated when the grating would appear relative to the cue. Some cues are predictive, in that the grating always appears after the same delay following the cue. Some cues are unpredictable, because they do not predict when the stimulus would appear. Subjects are instructed to use the cue to anticipate when the stimulus would appear. This is done while EEG data is recorded.

13. Sub-study Q: Speed of alpha oscillations and temporal resolution of perception measured with EEG

This sub-study addresses the question of whether there is a correlation between the speed of individuals' alpha oscillations (measured with EEG) and the temporal resolution of their perception. EEG data is recorded from a 60-channel cap connected to an Eximia 60-channel amplifier (Nextim, Helsinki, Finland) while subjects complete a two-flash fusion task. The task aims to determine the minimum time between two successive light flashes needed to perceive two, as opposed to one, distinct flashes. Subjects are seated 70 cm away from the monitor with a 100 Hz screen-refresh rate. Each trial begins with a central fixation cross (.98 degrees of visual angle) that reduces luminance to prepare subjects for the stimuli. The duration of the warning period is drawn from a uniform distribution between 1000 and 1500 ms. The fixation cross is present throughout the trial and the screen background is black. Grey disk stimuli are presented left or right of the fixation with equal probability and are always in the same location within a trial. Half of the trials are two-flash trials in which the first disk stimulus was present for 40 ms, followed by a blank screen of 10, 20, 30, 40 or 50 ms duration, followed by a 40 ms disk. The other half involves one-flash trials for which a single disk is presented. Subjects indicate whether they saw one or two flashes with a key press on a computer keyboard. The experiment takes 1.5 hours in total.

14. Sub-study R: Investigation of visual perception

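### Does sub-study AA lack the spatial and temporal expectation manipulation that its aim requires?

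*Protocol*

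**What the plan says.** Sub-study AA is described in protocol section 8.C.1.A, item 6, in four sentences. The first is the aim: "The aim of the study is to investigate how spatial and temporal expectation of forthcoming visual stimuli modulate both behaviour and brain oscillations". The second names the EEG equipment and a working-memory task on grating orientation. The third is the only description of what subjects see and do: "Each block consists of serial presentation of orientation grating stimuli with subjects indicating their memory for those stimuli". The fourth gives the session length.

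Sub-study Z, the item just before it, has another aim: "The aim of the study is to investigate the oscillatory and representational dynamics of contextual information in visual working memory". Its remaining three sentences are identical to AA's.

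Elsewhere AA appears only in lists: among the seven sub-studies on the title page, among the ongoing sub-studies in section 2, under Study Duration ("Sub-study AA: (SPACETIME EEG): One 3-4-hr visit for EEG session"), under Subject Population ("Sub-study AA: 30 subjects"), and in the heading of section 8.C. None of these describes the task.

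The objectives section says what separates one sub-study from another: "Specific experiments differ from one another in terms of the details of the cognitive task(s) that subjects perform".

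**The concern.** An expectation effect is a difference between trials on which the subject can and cannot anticipate where or when the stimulus will come. AA's aim names two such factors, and its task text names neither. The protocol treats task detail as the thing that distinguishes sub-studies, yet AA and Z have different aims, different sample sizes (30 and 24) and the same stated task.

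Other entries show that such detail can be given briefly. Completed sub-study P, in Appendix B, describes its timing manipulation: "Some cues are predictive, in that the grating always appears after the same delay following the cue", set against cues that carry no timing information. Sub-study AD describes its spatial cue: "an arrow will be presented for 200 msec as a cue to notice either the left or right side of the memory array".

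If AA's task really were the one written for Z, with nothing added, no trial would inform the stated question. AA is one of the seven sub-studies on the title page, so a whole named component would fail to address its aim.

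**Working it through.** The plan has no power calculation or other figure to reproduce for this point. The check compares texts, with some simple counts.

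**1. Is the text shared with Z?** Yes. After the aim sentence, both entries consist of the same three sentences: 26 words (equipment and task) + 18 words (stimuli and report) + 8 words (duration) = 52 words, an exact match.

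**2. Does AA's task text name a manipulation?** No. A search for eleven stems (cue, expect, predict, location, left, right, timing, interval, delay, probab, condition) finds none of them.

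**3. Is the shared text specific to Z?** No.
- The 26-word sentence also appears in full in sub-study AB.
- The 8-word sentence also appears in AC and AD.
- The first 10 words of the 18-word sentence open the matching sentence in Y, and its last 8 words close the matching sentence in AB: 10 + 8 = 18.

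So all 26 + 18 + 8 = 52 words recur in at least one entry other than Z. This is wording reused across neighbouring EEG-only entries. The match with Z does not show that AA was given Z's task.

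**4. What else does the entry leave out?** Trial and block numbers, stimulus duration, set size, delay length, inter-stimulus interval, stimulus position and form of response. The text cannot be run as it stands, for any purpose.

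**5. Do aim and task contradict each other?** No. Gratings shown in series with a memory report can appear at predictable or unpredictable positions and times, with or without cues. Nothing in the entry fixes position or timing or excludes a cue.

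**6. Is AA unusual?** No. Z's aim concerns contextual information, and its text states no context factor. AB's aim concerns transfer from working to long-term memory, and its text states no long-term memory test.

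**7. What would be affected if the manipulation were truly absent?**
- Session time: 30 × 3 h = 90 h to 30 × 4 h = 120 h.
- Share of the title-page sub-studies (L.3, O, Y, AA, AC, AD, AE): 24 + 24 + 42 + 30 + 24 + 30 + 25 = 199, and 30/199 = 15%.

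These figures give the size of AA. They would measure a loss only if the short entry were the complete design, which steps 4 and 5 do not support.

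**The case for a change.** The strongest argument for a change is that the manipulation is not an analysis detail. What subjects are exposed to belongs in the protocol, the section in question is the one for behavioural tasks, and by the protocol's own account the task defines the sub-study. P and AD show that a sentence or two would be enough. Without it, a reader cannot tell which levels of expectation were planned, and a contrast chosen later could be presented as the intended one.

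Part of this stands. The entry does not say how expectation is varied, and one cannot learn it elsewhere in the protocol.

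Two parts do not stand. First, the step from an unstated manipulation to a task without one: the document cannot show what the task contained, and the identical sentences are explained by reuse of stock text. Second, the claim that the contrast is left open to any choice: the aim fixes both factors (spatial and temporal expectation) and both kinds of outcome (behaviour and oscillations). How the contrast is formed may properly sit in an analysis plan, which is not at hand. Prescribing crossed cue conditions or a pre-stimulus power measure would replace the investigators' design with a reviewer's, since the aim calls for neither in particular.

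**Conclusion.** The concern does not hold as a fault in the plan. AA's entry is an incomplete summary in reused wording. It states no wrong rule or number and does not conflict with its own aim. What is missing is descriptive detail that the people running the experiment must settle before any session can take place, together with the trial counts, timings and display layout that are also unstated. Adding it would change no sample size, visit, procedure or analysis rule.

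This rests on one assumption: that a sub-study labelled SPACETIME, with an aim naming spatial and temporal expectation, varies both. The protocol neither confirms nor contradicts this. If the assumption were false, all 30 subjects (15% of the 199 in the title-page sub-studies, 90 to 120 session-hours) would give no information on the stated question, and a different task or a different aim would be needed. Nothing in the text beyond its silence points that way, so no change follows.

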Appendix A: Seizure Identification and Emergency Management

Seizure Identification

There are many different types of seizures. People may experience just one type or more than one. The kind of seizure a person has depends on which part and how much of the brain is affected by the electrical disturbance that produces seizures. Experts divide seizures into generalized seizures (absence, atonic, tonic-clonic, myoclonic), partial (simple and complex) seizures, nonepileptic seizures and status epilepticus.

Generalized – Generalized seizures affect both cerebral hemispheres from the beginning of the seizure. They produce loss of consciousness, either briefly or for a longer period of time, and are sub-categorized into several major types: generalized tonic clonic; myoclonic; absence; and atonic.

Partial – In partial seizures the electrical disturbance is limited to a specific area of one cerebral hemisphere. Partial seizures are subdivided into simple partial seizures (in which consciousness is retained); and complex partial seizures (in which consciousness is impaired or lost). Partial seizures may spread to cause a generalized seizure, in which case the classification category is partial seizures secondarily generalized.

Partial seizures are the most common type of seizure experienced by people with epilepsy. Virtually any movement, sensory, or emotional symptom can occur as part of a partial seizure, including complex visual or auditory hallucinations.

- **Simple** - People who have simple partial seizures do not lose consciousness during the seizure. However, some people, although fully aware of what's going on, find they can't speak or move until the seizure is over. They remain awake and aware throughout. Sometimes they can talk quite normally to other people during the seizure. And they can usually remember exactly what happened to them while it was going on. However, simple partial seizures can affect movement, emotion, sensations, and feelings in unusual and sometimes even frightening ways.
- **Complex** - Complex partial seizures affect a larger area of the brain than simple partial seizures and they affect consciousness. During a complex partial seizure, a person cannot interact normally with other people, is not in control of his or her movements, speech or actions; cannot control what he or she is doing; and does not remember afterwards what happened during the seizure.
- **Non-epileptic** – Non-epileptic seizures are episodes that briefly change a person's behavior and often look like epileptic seizures. The person having non-epileptic seizures may have internal sensations that resemble those felt during an epileptic seizure. The difference in these two kinds of episodes is often hard to recognize by just watching the event, even by

trained medical personnel. But there is an important difference. Epileptic seizures are caused by abnormal electrical changes in the brain and, in particular, in its outer layer, called the cortex. Non-epileptic seizures are not caused by electrical disruptions in the brain.

Status Epilepticus

Most seizures end after a few moments or a few minutes. If seizures are prolonged, or occur in a series, there is an increased risk of status epilepticus. The term literally means a continuous state of seizure and is considered a medical emergency. Status Epilepticus is defined as 30 minutes of uninterrupted seizure activity. An estimated 42,000 deaths and thousands more instances of brain damage per year follow episodes of status. Status epilepticus is most common in the very young and the very old, with the lowest incidence at ages 15-40.

Seizure Management

Convulsive Seizure

For individuals that experience generalized seizures, the following first aid should be provided in order to assure safety for all individuals involved and nearby.

- Keep calm and reassure onlookers.
- Don't hold the person down or try to stop his movements.
- Time the seizure with your watch.
- Clear the area around the person of anything hard or sharp.
- Loosen ties or anything around the neck that may make breathing difficult.
- Put something flat and soft, like a folded jacket, under the head.
- Turn him or her gently onto one side. This will help keep the airway clear. Do not try to force the mouth open with any hard implement or with fingers. It is not true that a person having a seizure can swallow his tongue. Efforts to hold the tongue down can injure teeth or jaw.
- Don't attempt artificial respiration except in the unlikely event that a person does not start breathing again after the seizure has stopped.
- Stay with the person until the seizure ends naturally.
- Be friendly and reassuring as consciousness returns.
- Contact on-call physician.
- If, at the discretion of the physician, the subject does not require admission to a hospital, accompany him/her to his/her home to insure that he/she arrives safely.

Non Convulsive

For individuals that experience non-convulsive, the following first aid should be provided in order to assure safety for all individuals involved and nearby.

- Watch the person carefully and explain to others what is happening. Often people who don't recognize this kind of behavior as a seizure think that the dazed person is drunk or on drugs.
- Speak quietly and calmly in a friendly way.
- Guide the person gently away from any danger, such as a steep flight of steps, a busy highway, or a hot stove. Don't grab hold, however, unless some immediate danger threatens. People having this kind of seizure are on "automatic pilot" so far as their movements are concerned. Instinct may make them struggle or lash out at the person who is trying to hold them.
- Stay with the person until full consciousness returns.
- Contact on-call physician.
- If, at the discretion of the physician, the subject does not require admission to a hospital, accompany him/her to his/her home to insure that he/she arrives safely.

Appendix B: Completed Studies Category A

1. Sub-study A: The role of parietal regions as sources of attentional control for spatial attention and spatial working memory.

The purpose of this study is to test the hypothesis that single pulses of TMS delivered to the superior parietal lobule (SPL) and intraparietal sulcus (IPS), areas implicated in the control of attention, will alter posterior task-related activity in a similar way for spatial delayed recognition as they do for spatial attention. More specifically, we predict that when subjects are attending to a location of space to, for example, the left of central fixation, the response evoked by a single pulse of TMS will be greater in magnitude in visual regions in the right hemisphere than in the left. The same pattern is predicted when subjects are remembering the locations of stimuli that had been presented to the left of fixation at the beginning of a delayed-recognition (i.e., “working memory”) task. Study A will combine a delayed-recognition task with a variant that requires spatial attention rather than spatial working memory. In the delayed-recognition task subjects will be presented with four dark-gray shapes appearing serially in four different locations on the (lighter gray) screen. The center of the screen is marked with a cross on which the subjects must keep their eyes throughout the trial. The stimuli are followed by a 8 second delay period, during which, on half of the trials, TMS is delivered. Finally, a white circle appears on the screen, and subjects indicate with a button press whether or not this probe appears in the same location as had one of the four shapes. In the spatial attention task, the fixation cross will rotate so as to point, throughout the delay period, to the location on the screen to which the subject should attend in order to detect a briefly presented, faint target that will appear with an unpredictable latency. The single pulse of TMS will be delivered with the same timing during both the working memory task and the attention task. During the inter-trial interval (ITI), the subject will perform a visuomotor tracking task that requires moving a cursor so that it stays on top of a moving target stimulus. The subject moves the cursor by pressing directional keys on a keypad. Performance is measured as the error between the position of the target and position of the cursor, as well as of the velocity of the cursor (e.g., if it stops moving).

Experimental Design: The design, 3 (task: attention; delayed recognition; no task) x 2 (visual field) x 2 (TMS: present, absent) factorial (modified to exclude empty and nonsensical cells), yields blocks/scans of 18 trials each. Single pulses of TMS, delivered at 110% of resting motor threshold intensity will be delivered to the right SPL, right IPS, and right postcentral gyrus (PoCG, a control area selected because it is not involved in the cognitive constructs under investigation). Stimulation will be blocked by region, with the order counterbalanced across subjects, with 3 consecutive blocks per region. (Total of 162 trials, 81 featuring TMS; therefore, total of 81 pulses delivered per experiment. Because trials are randomized with respect to whether or not a TMS pulse is delivered, the minimum time between pulses will be 18 sec (when pulses are delivered on two consecutive trials).)

2. Sub-study B.

Is the source of *object-based* attentional control the same for nonmemory attention tasks as for working memory tasks?

The attention task will present a flickering (750 msec on, 250 msec off) shape of approximately 1 degree of visual angle at central fixation, and the subject's task is to indicate with a button press each time a feature of the shape changes.

Shapes will be drawn from a set of polygons that have been normatively determined to be difficult to verbalize, and have been used in several of the PI's studies of object working memory. There are 4 variants of each shape, each of which differs by just one salient feature, and changes among the 4 will occur unpredictably an average of 3 times (range = 1 – 5) per trial. The delayed-recognition task will draw from the same pool of stimuli as the attention task, with invalid probes drawn from one of the 3 variants of the target shape from that trial. The regions to be targeted will be the frontal eye fields (FEF), a region previously targeted in two studies conducted under protocol H-2003-033, and the region from sub-study A that provide the most robust results, plus the leg area of somatosensory cortex in the postcentral gyrus (PoCG), an area used as a stimulation control area in many of the studies completed under protocol H-2003-033. During the inter-trial interval (ITI), the subject will perform a visuomotor tracking task that requires moving a cursor so that it stays on top of a moving target stimulus. The subject moves the cursor by pressing directional keys on a keypad. Performance is measured as the error between the position of the target and position of the cursor, as well as of the velocity of the cursor (e.g., if it stops moving).

Experimental Design: The design, 3 (task: attention; delayed recognition; no task) x 2 (visual field) x 2 (TMS: present, absent) factorial (modified to exclude empty and nonsensical cells), yields blocks/scans of 18 trials each. Single pulses of TMS, delivered at 110% of resting motor threshold intensity will be delivered to the right FEF, right SPL or IPS, and right PoCG. Stimulation will be blocked by region, with the order counterbalanced across subjects, with 3 consecutive blocks per region. (Total of 162 trials, 81 featuring TMS; therefore, total of 81 pulses delivered per experiment. Because trials are randomized with respect to whether or not a TMS pulse is delivered, the minimum time between pulses will be 18 sec (when pulses are delivered on two consecutive trials).)

3. Sub-study C.

Further investigation of the mechanisms of *object-based* attentional control and its relation to object working memory.

The logic will be to cross two stimulus types – faces and houses – with two task types – attention and working memory. Tokens of the two stimulus types will always be presented superimposed at central fixation, a procedure that has been used to demonstrate that object-based attention can selectively bias activity in regions associated with processing either stimulus type, depending on task instructions. The responses evoked by TMS pulses during task performance will ascertain whether the targeted regions are a source of object-

based attentional selection by indicating whether TMS pulses have differential effects on face-selective vs. house-selective cortex as a function of task instructions. The regions to be targeted will be the same as those from Study B. During the inter-trial interval (ITI), the subject will perform a visuomotor tracking task that requires moving a cursor so that it stays on top of a moving target stimulus. The subject moves the cursor by pressing directional keys on a keypad. Performance is measured as the error between the position of the target and position of the cursor, as well as of the velocity of the cursor (e.g., if it stops moving).

Experimental Design: The design, 3 (task: attention; delayed recognition; no task) x 2 (visual field) x 2 (TMS: present, absent) factorial (modified to exclude empty and nonsensical cells), yields blocks/scans of 18 trials each. Single pulses of TMS, delivered at 110% of resting motor threshold intensity will be delivered to the three from sub-study B. Stimulation will be blocked by region, with the order counterbalanced across subjects, with 3 consecutive blocks per region. (Total of 162 trials, 81 featuring TMS; therefore, total of 81 pulses delivered per experiment. Because trials are randomized with respect to whether or not a TMS pulse is delivered, the minimum time between pulses will be 18 sec (when pulses are delivered on two consecutive trials).)

4. Sub-study D. Comparing the effects on spatial working memory of repetitive TMS delivered at multiple frequencies (MRI-guided)

This study modifies the procedure of the working memory task from *sub-study A* by shortening the delay period to 3 sec, simultaneously recording the EEG, including three EEG sessions, and varying the frequency at which repetitive TMS is delivered, so as to compare the effects of repetitive TMS delivered at 10 Hz, IAF+1Hz, and the frequency of sustained delay-period oscillatory power in the 10 - 20 Hz range. In this sub-study subjects will be presented with four dark-gray shapes appearing serially in four different locations on the (lighter gray) screen. The center of the screen is marked with a cross on which the subjects must keep their eyes throughout the trial. The stimuli are followed by a 3 second delay period, during which, on half of the trials, repetitive TMS is delivered.

Finally, a white circle appears on the screen, and subjects indicate with a button press whether or not this probe appears in the same location as had one of the four shapes. The three frequencies are of interest for varying reasons: 10 Hz is the frequency at which repetitive TMS has been delivered on all of our previous studies of spatial working memory, and comparison of results with the other two frequencies vs. the “gold standard” of 10 Hz will thus be very informative. IAF+1 Hz is the frequency at which Klimesch et al. (2003) have reported facilitatory effects of repetitive TMS, and offers a parameter by which repetitive TMS frequency can be tailored to the physiology of individual subjects. Sustained delay-period oscillatory power has been observed in many published EEG studies, including *Hamidi, M., Slagter, H.A., Tononi, G., and [name], B.R. (2009). Repetitive transcranial magnetic stimulation affects behavior by biasing endogenous cortical oscillations. Frontiers in Integrative Neuroscience, 3:14. doi:10.3389/neuro.07.014.2009. PMC2707056*. Thus, it offers a second task-

related parameter by which repetitive TMS frequency can be tailored to the physiology of individual subjects. As indicated above, the sub-study will include three EEG sessions. The first will be the brief “eyes open/eyes closed” session to determine IAF, the second will entail repetitive TMS at 10 Hz and at IAF +1, the third, repetitive TMS at 10 Hz and at the frequency of sustained delay-period oscillatory power. The reason for using 10 Hz during two sessions is that although previous studies have revealed individual differences in the effects of repetitive TMS on both behavior and task-related EEG (Hamidi et al., 2009; Sub-study L), we do not yet know whether these patterns of individual differences are stable over time. That is, if 10 Hz repetitive TMS produces an increase in alpha-band power and a decrease in accuracy for subject #1, and a decrease in alpha-band power and an increase in accuracy for subject #2 (mirroring what we saw in Hamidi et al (2009)), will these same two subjects show similar effects if they perform the same experiment on a different day? In other words, what is the test-retest reliability of our procedure? The third session will occur on a different day than the second.

Experimental Design: Repetitive TMS will be delivered in 1.2 sec-long trains of 10 Hz, IAF +1, and sustained delay-period oscillatory power, at 110% of the resting motor threshold intensity, at the beginning of the delay period. There will be a 5 second interval between all trials.

5. Sub-study E. The effects on spatial working memory of repetitive TMS delivered at a region’s natural frequency (MRI-guided)

The natural frequency of a corticothalamic circuit is the frequency with which a brain region oscillates when stimulated by a pulse of TMS (analogous to the “ringing” that results from striking a bell, Rosanova et al., 2009). For the superior parietal lobule (SPL) this corresponds to 20 Hz. The SPL has been the target of most of our previous repetitive TMS studies of spatial working memory, and 10 Hz repetitive TMS of the SPL has produced interesting behavioral and EEG results (i.e., Hamidi et al., 2008; 2009). The purpose of this sub-study is to compare the results of repetitive TMS of SPL at 10 Hz with those of repetitive TMS of SPL at this region’s natural frequency, which can vary between 18 – 24 Hz depending on the individual. At issue is whether the natural frequency reflects a functional property of a region, or whether it is merely a byproduct of a region’s corticothalamic architecture that does not influence that region’s function. The procedure for Sub-study E will replicate that of Sub-study D, with the exceptions that there will be two sessions (instead of 3; Session 1 will entail IAF estimation and natural frequency estimation, and Session 2 will entail task performance), and repetitive TMS will be delivered concurrent with behavioral task performance at IAF +1 and at the subject’s natural frequency.

Experimental Design: Depending on the natural frequency of SPL for a given subject, all repetitive TMS trains will be delivered for either 1.2 sec (if natural frequency \leq 20 Hz) or 0.7 sec (if natural frequency $>$ 20 Hz and \leq 25 Hz), at frequencies of IAF+1Hz and of the subject’s natural frequency, at 110% of the

resting motor threshold intensity, at the beginning of the 3 sec-long delay period. There will be a 5 second interval between all trials.

6. Sub-study F. The effects of cognitive training on sustained delay-period brain activity.

Analyses of data from two previous studies performed by the PI's group under protocol H-2003-033 indicate that there are considerable individual differences in the patterns of sustained delay-period oscillations as measured by EEG. The nature of these differences is intriguing, because they are present despite the fact that all subjects are performing the same task, and are generally doing so at the same level of proficiency. They raise such question as: *Do these differences underlie individual differences in behavior? Do they reflect differences in the cognitive processes engaged by different individuals, or, instead, perhaps differences in trait-like physiological profiles that do not relate directly to task performance?* Answers to these questions will contribute importantly to understanding which elements of sustained delay-period oscillations are critical for working memory-task performance. The strategy for addressing these questions, to be implemented in this sub-study, will be twofold: a) administer several psychometric tests that measure important cognitive and affective traits, and evaluate which covary with sustained delay-period oscillations; and b) assess the effects on sustained delay-period oscillations of a 5 week-long course of cognitive training on a working memory task. Previous work indicates that such training can produce improvement on working memory-task performance that generalizes to other cognitive domains (e.g., Olesen et al., 2004). Our question will be which, if any, aspects of sustained delay-period oscillations are also sensitive to cognitive training. Thus, there are three categories of behavioral task in this sub-study: the *EEG* and *TMS-EEG tasks* during which sustained delay-period oscillations are measured, the *psychometric tasks*, and the *training task*.

